S13-00448: Uncontrolled Lower Respiratory Symptoms in the WTC Survivor Program NCT02024204

Principal Investigator: [name]

*Co-Investigators: [name]
[name]
[name]
[name]
[name]
[name]
[name]
[name], MA
[name], BA
[name]
[name], BA*

Purpose of the Study

Exposure to the dust and fumes of the World Trade Center (WTC) disaster resulted in adverse health including upper and lower respiratory symptoms in responders and community members. The WTC Environmental Health Center (WTC EHC), initiated in 2005, was the first and remains the only treatment program that targets community members, now called “Survivors,” including local residents, local workers and clean-up workers with WTC dust and fume exposures { }. Lower respiratory symptoms (LRS) that include cough, wheeze, dyspnea, and chest tightness are prevalent in patients in the WTC EHC. Most patients with these symptoms in the “Responder” and “Survivor” programs are diagnosed with asthma and this diagnosis has guided therapy. Although spirometry is often normal, diagnosis has been supported by studies showing bronchial hyperresponsiveness (BHR) in some { } { }, and distal or small airways disease measured with impulse oscillometry (IOS) { } { }. As a result, the WTC EHC program has used a treatment algorithm based on guidelines for asthma from the National Institutes of Health ¹. These guidelines focus on the use of “controller” therapy, which includes inhaled corticosteroids (ICS) and long acting bronchodilators (LABA) for persistent symptoms. Despite this approach, **eleven years after the destruction of the WTC towers, many patients in the WTC EHC report incomplete clinical response with continued lower respiratory symptoms.** In fact, patients with continued uncontrolled lower respiratory symptoms (LRS) remain on treatment with long-term high dose ICS often with additional LABA use, rendering them at risk for adverse health effects of long term ICS treatment. The persistence of symptoms, despite therapeutic interventions, necessitates a reevaluation and a search for causes of persistent symptoms. Possibilities include incomplete adherence with medical regimens, continuing airways disease (BHR or small airways disease) with persistent lung inflammation, or the presence of co-morbid conditions. **Our overall hypothesis is that WTC EHC patients with uncontrolled LRS despite aggressive medical therapy have increased rates of abnormal airway physiology, airway inflammation and co-morbid conditions. Identifying mechanisms for uncontrolled LRS is imperative to guide therapy with the important potential to reduce secondary adverse health outcomes.** We will test this hypothesis using a prospective study with the following aims:

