
Specific Aim 1. To conduct a clinical study with aggressive treatment for lower respiratory symptoms in the WTC EHC in order to identify a group of patients with controlled lower respiratory symptoms (CLRS) and a group of patients with persistent uncontrolled lower respiratory symptoms (ULRS).

SA1.a To test whether a three month treatment with combined high dose inhaled corticosteroids (ICS) and long acting bronchodilators (LABA) results in improved lower respiratory symptoms in patients overall.

Specific Aim 2. To test the hypothesis that discrete measures of lung physiology are associated with the status of ULRS and CLRS in patients in the WTC EHC.

SA2.a To test whether bronchial hyperresponsiveness (BHR) is associated with the status of ULRS and CLRS by comparing rates of BHR in patients with ULRS and CLRS.

SA2.b To test whether measurements of airflow and lung volume (FEV₁, FVC, FEV₁/FVC, RV/TLC) and of small airway dysfunction (impulse oscillometry) are associated with ULRS and CLRS status.

Specific Aim 3. To test the hypothesis that inflammatory markers associated with airway disease are increased in patients with ULRS compared to CLRS in the WTC EHC.

SA3.a Compare levels of an exhaled marker of inflammation (Fractional exhaled nitric oxide; FeNO) in patients with ULRS and CLRS.

SA3.b Compare levels of circulating biomarkers associated with a Th2 inflammatory response (total and allergen-specific IgE, circulating eosinophils, C-reactive protein, serum periostin) in patients with ULRS and CLRS.

Specific Aim 4. To test the hypothesis that increased rates of co-morbid conditions are associated ULRS compared to CLRS in the WTC EHC.

SA4.a Compare quantitative measures of PTSD, anxiety or depression in patients with ULRS and CLRS.

SA4.b Compare rates of chronic rhinosinusitis symptoms and probable paradoxical vocal cord motion (PVCM) in patients with ULRS and CLRS.

SA4.c Compare rates of gastroesophageal reflux symptoms in patients with ULRS and CLRS.

Background

Exposure to WTC dust/fumes/gas in the “Survivor” population

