2x/week in the month preceding the monitoring visit. LRS will include: wheeze, shortness of breath at rest or with mild exertion, or chest tightness. These criteria for inclusion will be confirmed during V1 with a repeat questionnaire.

Sampling strategy for screening and enrollment in V1. Patients will be recruited from the WTC EHC population using block stratification *a priori* to obtain a representative sampling of the monitoring population (i.e. 5 patients with recent monitoring visits, 5 patients with monitoring visits > 1 year previously). The sampling will not be stratified by race/ethnicity, age, and exposure but these variables will be adjusted in statistical analyses. We anticipate that we will telephone 300 patients for our final enrollment of 200 patients for the study.

Inclusion/Exclusion criteria. Detailed inclusion/exclusion criteria for subject identification for potential

enrollment include:

- Onset of LRS after 9/11/01
- Presence of LRS > 2x/week in the month preceding the monitoring visit at chart review of the WTC EHC Monitoring visit **and confirmed in V1**
- Absence of abnormal CXR or other lung disease
- ACT score ≤ 19 at monitoring visit

Detailed exclusion criteria for potential enrollment include:

- Presence of abnormal CXR
- Presence of other lung disease (e.g. ILD, sarcoidosis)
- Current or ≥ 5 p-y tobacco use
- ACT score ≥ 20 at monitoring visit

A study scheme and procedure chart is shown:

Telephone screening visit (SV)

Patients with persistent LRS will be identified from the WTC EHC data base and will be contacted by telephone or in person. Study will be described and interest in study will also be determined.

Enrollment visit (V1)

Control status will be assessed with the Asthma Control Test (ACT), a symptom-based validated instrument^{76, 77}. Questionnaires to assess detailed specific respiratory symptom frequency, current environmental exposures, and severity and co-morbid conditions of PTSD/depression/anxiety will be administered. The Modified Medical Research Council (MMRC) dyspnea scale will be completed to assess degree of dyspnea. Baseline FeNO (fractionated exhaled Nitric Oxide) and pre and post bronchodilator (bd; 360 mcg albuterol) spirometry and IOS will be obtained.

Patients will be treated in the following manner based on assessment at V1:

- Patients who have uncontrolled LRS (ACT < 20) at time of this visit will be provided with study Advair for a total of 3 months.

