	Screening	V1 (enrollment)	V2	V3	V4
Time (weeks)		1	4	8	12
Consent		X			
Inclusion/exclusion	X	X			
Study review	X	X			
ACT		X	X	x	X
Physical Exam		X			
FeNO		X			X
Spirometry (pre/post bd)		X			X
IOS (pre/post bd)		X			X
Adherence counseling		X	X	X	
Daily diary review		X	X	X	
Medication distribution		X	X	X	
Classification confirmation		X			X
Co-morbid Medical Questionnaire (GSAS,SSS)			X		
Vocal Handicap Index					X
Respiratory questionnaire (ASUI)		X			X
Mental Health Questionnaires (SF12V2, PHQ, PCL)		x			x
MMRC Dyspnea Scale		X			X
VCD assessment					X
MCT				X	
Pregnancy test		X		X	
Blood		X			
AE screen			X	X	X
Leicester Cough Questionnaire				X	
Urine Sample for Cotinine				X	
6 minute walk test				x	

- Patients who have uncontrolled LRS at V1, but do not fit criteria for Step 3,4 or 5 asthma therapy according to NIH EPR III asthma guidelines will be deferred from the study until they have been seen by their physician and tried on ICS therapy.
- Patients who had symptoms at monitoring visit but are now controlled at V1 will be asked to continue their current treatment (or no treatment) and will continue with the study. They will not be provided with any medications.

Study medication will be provided as open label high dose ICS/LABA diskus (fluticasone /salmeterol; 500/50 mcg; 1 inhalation twice daily, or MDI 230/21, 2 puffs bid) for a 1 month period. Inhaler training and adherence counseling will be performed. Patients will be instructed to maintain a daily diary.

Adherence visit (V2) Patients will return for a monthly visit. At this visit the study will be reviewed, inhaler technique reviewed, and adherence counseling administered. Notation of the counter denoting actuation of the ICS/LABA diskus will be made to assess adherence. Daily diary will be reviewed. Patients will be queried for any adverse effects. Questionnaires to assess co-morbid conditions of chronic rhinosinusitis, and gastroesophageal reflux (GER) will be administered as well as the ACT to assess for control status

Adherence visit (V3) This visit will be similar to V2, however, a methacholine challenge test with lung volumes and oscillometry will also be performed on all patients. Patients will complete the Leicester Cough Questionnaire at Visit 3. Urine will be obtained for cotinine measurements. as well as the ACT to assess for control status

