Classification visit (V4): After 3 months, patients will return for their Classification. At this visit, medication use will be reviewed by noting the medication actuations, and ACT and disease-specific questionnaires for asthma control (ASUI) will be completed^{78, 79}. Screening instruments for post-traumatic stress disorder (PTSD), depression and anxiety will be completed. Blood will be obtained for total and allergen specific IgE, peripheral eosinophil measurements, and measurements of serum periostin and C-reactive protein. FeNO, pre and post BD spirometry and IOS will be performed. Patients will complete a 6 minute walk test. Patients will also undergo laryngoscopy and vocal cord assessment. If patients are unable to complete the vocal cord assessment on the same day as V4, they will be asked to return for a separate visit within two weeks of the end of study (Day 76-90) and will be compensated \$100 for this additional time and effort.

Control Classification. Patients will be classified as ULRS or CLRS based on the ACT score obtained at V4.

Specific Aim 2. To test the hypothesis that discrete measures of lung physiology are associated with patients in the WTC EHC with ULRS compared to CLRS.

Preliminary data pertinent for SA2.

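### The controlled group at V4 mixes patients already controlled at V1, who get no study drug, with responders to study ICS/LABA, and no treated-only analysis is planned; this matters mainly for bronchial hyperresponsiveness

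*Combined protocol and SAP*

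**What the plan says.** Under Enrollment visit (V1), patients with an ACT score below 20 "will be provided with study Advair for a total of 3 months". The treatment rules that follow the visit table add a second route: "Patients who had symptoms at monitoring visit but are now controlled at V1 will be asked to continue their current treatment (or no treatment". These patients remain in the study, and "They will not be provided with any medications".

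Control Classification then applies one rule to both routes: "Patients will be classified as ULRS or CLRS based on the ACT score obtained at V4". V1 status and receipt of study drug play no part in it.

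The aims are worded in two ways. Specific Aim 2 asks whether "discrete measures of lung physiology are associated with the status of ULRS and CLRS", which is a plain association. The overall hypothesis in Purpose of the Study is that "WTC EHC patients with uncontrolled LRS despite aggressive medical therapy have increased rates of abnormal airway physiology, airway inflammation and co-morbid conditions". Specific Aim 1 describes "aggressive treatment for lower respiratory symptoms in the WTC EHC in order to identify a group of patients with controlled lower respiratory symptoms (CLRS" and the matching uncontrolled group, so the groups are meant to emerge from treatment.

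Statistical analysis of the data compares ULRS with CLRS by chi-square, Wilcoxon and logistic regression. Its list of confounders is open-ended; it names age, gender, BMI and WTC exposures, but neither V1 control status nor study drug. Sample size estimation mentions an intention-to-treat analysis that includes drop-outs. No analysis restricted to treated patients is described.

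**The concern.** One label covers two kinds of patient. CLRS holds those who became controlled on high-dose ICS/LABA and those who were controlled before the study gave them anything and stayed so. V1-controlled patients reach ULRS only if they worsen, so they fall unevenly across the two groups.

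The BHR section of SA2.a makes this matter. It says ICS may reduce BHR without necessarily normalizing it. It also describes all patients as having had two months of study therapy when methacholine challenge is done at V3, which the V1 treatment rules contradict. If the two routes differ in BHR, a pooled difference, or the lack of one, partly reflects route. CLRS could then not be read as responders to aggressive therapy.

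FeNO is a weaker case. SA3.a links higher FeNO to corticosteroid responsiveness, so it may mark who responds, but does not say that ICS changes it.

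**Working it through.** **The plan's own figures.** Sample size estimation expects 120 ULRS and 80 CLRS of 200. It states 80% power for an odds ratio (OR) of 2.08 with a 30% rate in CLRS, and for an OR of 1.498 per SD of a continuous covariate.
- Continuous: exp((1.960 + 0.842)/√(200 × 0.6 × 0.4)) = 1.498, which reproduces (two-sided 0.05).
- Categorical: OR 2.08 means 47.1% vs 30%. The normal-approximation power is 79% one-sided and 68% two-sided, so the stated 80% fits a one-sided test. Two-sided, the detectable OR at 120/80 is 2.30 (exact enumeration of the chi-square test, no continuity correction). I use that basis below only to put different group sizes on one footing.

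**Inputs for the mixing calculation.**
- From the plan: N = 200; 40% controlled at V4; 30% event rate in CLRS.
- Assumed: the 40% applies to treated patients; share c controlled at V1 of 10%, 20% or 30%; 80% of those still controlled at V4; BHR rate q in V1-controlled patients. The documents give none of these.
- Scenario A: treated ULRS 46.15%, treated CLRS 30%, so the treated OR is 2.0.
- Scenario B: 40% BHR in both treated groups, so the treated OR is 1.0.

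**Formulas.** V1-controlled patients V = 200c; treated patients T = 200 − V. CLRS contains 0.4T treated and 0.8V V1-controlled; ULRS contains 0.6T and 0.2V. The BHR rate in each group is the average weighted by these counts, and pooled OR = odds(ULRS)/odds(CLRS).

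**Worked case: c = 20%, A, q = 20%.** V = 40, T = 160. CLRS = 64 + 32 = 96; ULRS = 96 + 8 = 104.
- CLRS rate = (64 × 0.30 + 32 × 0.20)/96 = 0.267
- ULRS rate = (96 × 0.4615 + 8 × 0.20)/104 = 0.441
- OR = (0.441/0.559)/(0.267/0.733) = 2.17

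| Share c | Treated ULRS/CLRS | V1-controlled in ULRS/CLRS | A, q=20% | A, q=40% | B, q=20% | B, q=50% |
|---|---|---|---|---|---|---|
| 10% | 108/72 | 4/16 | 2.10 | 1.82 | 1.13 | 0.94 |
| 20% | 96/64 | 8/32 | 2.17 | 1.68 | 1.25 | 0.90 |
| 30% | 84/56 | 12/48 | 2.21 | 1.57 | 1.35 | 0.87 |

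**Sensitivity to the layout.** Holding the totals at 120/80 instead gives wider shifts in A: 2.13 and 1.81 at 10%, 2.27 and 1.64 at 20%, 2.44 and 1.49 at 30%. But that forces the control rate among treated patients down to 64/180 = 36%, 48/160 = 30% and 32/140 = 23%, so I do not rely on it.

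**FeNO.** If V1-controlled patients differed by an assumed 0.5 SD of log-FeNO and the treated groups did not differ, the pooled difference is 0.5 × (V1-controlled fraction of CLRS − that of ULRS): 0.5 × (16/88 − 4/112) = 0.07 SD at 10%, 0.13 at 20% and 0.17 at 30%.

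**Precision of a treated-only subset at c = 20%.** With 96/64 the detectable BHR OR is 2.54. With 112/48 (the fixed-total layout) it is 2.70, and 1.62 per SD for FeNO. The 95% interval around OR 2.0 at 112/48 uses SE(log OR) = √(1/(112 × 0.4615 × 0.5385) + 1/(48 × 0.30 × 0.70)) = 0.368, giving about 0.97 to 4.1.

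**The case against.** **It is a choice of comparison, not an error.** Aims 2 to 4 compare patients by status, and the overall hypothesis defines only the uncontrolled group, which in the table is 87% to 96% treated. This stands as a reason to keep the pooled analysis. It does not supply the comparison that Aim 1 sets up, in which both groups come out of treatment.

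**The V1-controlled group may be very small.** On persistent symptoms the protocol says: "These criteria for inclusion will be confirmed during V1 with a repeat questionnaire". That could remove most such patients. The concession stands, and no passage supports shares of 20% or 30%. Still, the plan has a dedicated rule for keeping these patients, and it samples deliberately from those last monitored more than a year ago.

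**The subset cannot settle the matter.** An interval of about 0.97 to 4.1 covers every pooled OR in scenario A. This also stands: the subset is supportive only, and the counts by V4 group may be as informative.

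**It is partly handled already.** The covariate list is open, and V1 ACT and medication distribution are scheduled. That makes the fix cheap; it does not make the analysis prespecified, and the treatment is open label.

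**Stronger readings that the documents do not support.**
- A reader might infer that the pooled analysis is invalid. It is not; it answers a question about V4 status.
- A reader might take V1-controlled patients as untreated. The background says many clinic patients remain on substantial ICS, while the sample-size section assumes many had stopped, were on little or were non-adherent. Either is possible, so the direction is open.
- A reader might infer that study drug shifts FeNO. SA3.a does not say so.
- A reader might extend the point to the Aim 4 co-morbidities. The documents state no effect of ICS on them.

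**Conclusion.** The concern holds in limited form. As written, the plan never separates response to study ICS/LABA from control that was already present at V1, so the pooled ULRS-CLRS contrast does not isolate symptoms uncontrolled despite aggressive therapy. BHR is the measure at issue, with FeNO second.

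The size depends on a share that the documents do not give. If 40% of treated patients and 80% of V1-controlled patients are controlled at V4, and BHR in the latter is 20% to 40%, the gap from a treated OR of 2.0 is slight at a 10% share and could change interpretation from about 20%. The shift can go either way. The V3 sentence in SA2.a is wrong whatever the share. The change is worth making; leaving it out would not invalidate the planned comparisons.

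**What to change.** 1. Keep the pooled ULRS-CLRS analysis as primary.
2. Prespecify one supportive sensitivity analysis with the methods already planned, restricted to patients uncontrolled at V1 who received study ICS/LABA, for BHR first and FeNO second.
3. Report how many V1-controlled patients fall in each V4 group. Do not test ULRS against CLRS among them; 8 vs 32 at a 20% share is too few to inform.
4. Correct the BHR text in SA2.a to say that only patients uncontrolled at V1 will have had two months of study therapy at V3.

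The cost is one subset analysis, one small table and one sentence. The V1 ACT and medication distribution are already scheduled, and current therapy is probably known from the Step 3 to 5 eligibility assessment. The downside is precision: at a 20% share the subset is 96 vs 64 or 112 vs 48 depending on the assumptions, with a detectable BHR OR of about 2.5 to 2.7 against 2.30 for 120 vs 80 on the same two-sided basis. It therefore supports the pooled result and does not replace it.

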often consistent with small or distal airway dysfunction²⁸. The diagnosis of asthma is a clinical diagnosis based on a constellation of clinical findings and lung function measurements^{1,29}, and thus we have treated patients with LRS and a normal CXR with normal, obstructive, or a reduced VC as if they had asthma according to asthma treatment guidelines¹. Treatment of persistent symptoms is initiated with an anti-inflammatory controller agent, predominantly ICS with long acting bronchodilators (LABA) added as a step-up medication for uncontrolled symptoms¹. **Since only a limited number of patients have undergone methacholine challenge, we define these patients in this proposal as having LRS rather than providing a diagnosis of “asthma.”**

Management of co-morbid symptoms. Co-morbid conditions (gastroesophageal reflux; GER, chronic rhinosinusitis, PTSD/depression/anxiety) are also attended to with a treatment algorithm. GER symptoms are treated with a proton pump inhibitor, and if persistent, patients are referred to a gastroenterologist. Chronic rhinosinusitis is treated with nasal steroids, saline washes and if persistent, these individuals undergo sinus CT scans and are referred to a specialist. Patients who score positive for PTSD/depression/anxiety are referred to our mental health program, where they undergo further diagnostic evaluation and are provided with appropriate therapy.

Continued LRS in the WTC EHC

To understand the course of illness in the WTC, we recently examined longitudinal lung function and symptoms. Examination of longitudinal spirometry measurements in the WTC EHC suggests that many spirometric parameters improved over time³⁰. However, our review of the presence of persistent LRS (present > 2 x/week in the preceding month) in the first patients who returned for a standardized monitoring examination (n = 1300), shows that LRS symptoms continue: 56% had persistent cough, 32% had wheeze and 50% had any LRS other than cough (Table 1; unpublished data). Thus, the WTC EHC now includes a cohort of patients with persistent LRS symptoms, many of whom remain on substantial doses of ICS. The continued use of high dose ICS puts these patients at risk for corticosteroid associated complications³¹. **The continued nature of the LRS despite treatment with high dose medications necessitates a re-evaluation of the disease process in this population.**

Lung physiology in WTC-exposed patients without other lung disease

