We will enroll patients from our adult clinic which includes patients ≥ 18 years of age (NIH definition of children is < 21) and will include patients up to age 75. Above age 75, there are few normal values for lung function testing.

Racial and Ethnic Origin

We will enroll subjects with the race/ethnic distribution of the data from our monitoring results in the WTC EHC clinic, which is approximately 40% Hispanic, 20% Black, 6% Asian.

Inclusion Criteria

Age ≥ 18 years and <75

Meet criteria for WTC EHC enrollment

Onset of LRS after 9/11/01

Persistent LRS at chart review of WTC EHC Monitoring visit

Pre-bd FEV1 within normal limits at chart review of WTC EHC Monitoring Visit

≤ 5 p-y tobacco

Not current smoker

Asthma Control Test Score ≤ 19 at chart review of WTC EHC Monitoring Visit

Normal CXR

Exclusion Criteria

Age < 18 years and Age ≥75
LRS or asthma history pre 9/11/01
No persistent LRS
pre-bd FEV1 below the lower limit of normal (NHANES)
> 5 p-y tobacco
Current smoker
Asthma Control Test Score ≥20

Abnormal CXR or parenchymal changes on HRCT

Uncontrolled major chronic illness (DM, CHR, cancer, mental health)

History of significant non-WTC occupational or environmental exposure

Allergy to study drug

Pregnancy, lactation or plans to become pregnant

Chronic oral corticosteroids

High risk of fatal or near-fatal asthma within previous 2 years

Other lung disease (IPF, sarcoid etc.)

Vulnerable Subjects

N/A

Methods & Procedures

Methods & Procedures

SA1.a To test whether a three month treatment with combined high dose inhaled corticosteroids (ICS) and long acting bronchodilators (LABA) results in improved LRS.

Trial Scheme. Subject recruitment and a trial scheme visit schedule is shown in Fig 1.

Database Pre-screening. Pre-screening will be used for initial subject recruitment. [name] is a member of the WTC EHC Data Center, and will work in collaboration with the WTC EHC Data Center (collaboration letter included). Only patients who have agreed to be re-contacted will be included. Information on symptom frequency will be obtained from data from the standardized “monitoring” visit. Patients with persistent LRS will be invited for an Initial Visit (V1).

Definition of persistent LRS. We define “persistent LRS” based on definitions for the NIH asthma guidelines as LRS that occurs >

[Fig. 1. Trial visit scheme.](#)

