Sample size estimation

Our primary outcome will be the rate of LRS and CLRS after the 3 month adherence period (SA1). We base our sample size and recruitment on our initial analysis of the WTC EHC monitoring in which 88% of patients who had ever received ICS or ICS/LABA had an ACT score of ≤ 19 . We assume however, that many of these patients were either no longer using medication at the time of the assessment, were on minimal dose, or were non-adherent. Thus we predict by V4 that we will have a 60% rate of ULRS and a total of 200 patients would yield 120 patients who will fit criteria as ULRS and 80 as CLRS. To take into account potential screen failures and dropouts, we will approach 300 patients initially to obtain the total sample size of 200. We will include drop-outs in our intention to treat analysis as these patients can be considered for baseline analysis.

For categorical endpoints, such as BHR, PTSD and PVDMM, the sample sizes of 120 in ULRS group and 80 in CLRS group will achieve 80% power to detect an odds ratio of 2.08 at significance level of 0.05, assuming that the rate of disease is 30% in the CLRS group. A logistic regression of the ULRS vs. CLRS on a continuous,

normally distributed variable (such as depression score or log-FeNo) with a sample size of 200 observations will achieve 80% power at a 0.05 significance level to detect an OR of 1.498 for 1- standard deviation (SD) difference in the continuous covariate.

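### SA1.a asks whether treatment improves LRS, but no V1-to-V4 analysis is planned, and the frequency measure that defines persistent LRS is not named at V4

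*Combined protocol and SAP*

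**What the plan says.** The combined protocol and SAP works with two symptom constructs.

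- **Persistent LRS** is a frequency. Under Definition of persistent LRS it is set "based on definitions for the NIH asthma guidelines as LRS that occurs >" "2x/week in the month preceding the monitoring visit. LRS will include: wheeze, shortness of breath at rest or with mild exertion, or chest tightness". The detailed inclusion list requires "Presence of LRS > 2x/week in the month preceding the monitoring visit at chart review of the WTC EHC Monitoring visit", and the definition adds: "These criteria for inclusion will be confirmed during V1 with a repeat questionnaire".
- **Uncontrolled LRS** is an ACT score. Entry requires "ACT score ≤ 19 at monitoring visit", and Enrollment visit (V1) equates uncontrolled LRS with an ACT below 20.

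At V1, patients with uncontrolled LRS receive study drug for three months, apart from those deferred because they do not meet the asthma-therapy step criteria. Patients whose symptoms are controlled by V1 stay in the study on their existing treatment, or none, and receive no study medication.

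For the end of the study, Control Classification says: "Patients will be classified as ULRS or CLRS based on the ACT score obtained at V4". The V4 text names the ACT and the ASUI as its respiratory symptom instruments, and the procedure chart also marks the MMRC dyspnea scale at V4.

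SA1.a sets out to test whether the treatment improves LRS. Sample size estimation makes the V4 rate of the two classes the primary outcome for SA1. Statistical analysis of the data describes only comparisons between ULRS and CLRS.

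**The concern.** An aim about improvement needs a before-and-after contrast in the people who were treated. The plan offers a single proportion at V4. Its denominator includes people who received no study drug and who were already controlled when the treatment period began, so it is not a treatment result even descriptively.

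There is also a question of meaning. Patients are recruited because symptoms occur more than twice a week, but that measure is not named again after V1. A patient with a V4 ACT of 20 or more who still has symptoms that often is labelled controlled. A patient with a low ACT and infrequent symptoms is labelled uncontrolled. All SA2 to SA4 comparisons use this label, so it matters how far it agrees with the entry definition. If the frequency items are not asked at V4, the information cannot be recovered later.

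**Working it through.** **1. Measures set side by side** (visit text, procedure chart, Sample size estimation, Statistical analysis of the data)

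| Measure | Role at entry | V1 | V4 | Use in an SA1 analysis |
|---|---|---|---|---|
| LRS more than 2x/week | defines persistent LRS | yes, repeat questionnaire | not named; may sit in the ASUI row | none |
| ACT | 19 or less required; below 20 is uncontrolled | yes (also V2, V3) | yes | V4 class only |
| ASUI | none | yes | yes | none |
| MMRC dyspnea | none | yes | yes | none |
| Daily diary | none | review marked (also V2, V3) | review not marked | none |

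Three symptom instruments are therefore paired between V1 and V4, but none is assigned to SA1.a as a change measure and no within-patient test is named.

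**2. The plan's own figure.** 200 x 0.60 = 120 ULRS and 200 x 0.40 = 80 CLRS, which reproduces the stated split. The standard error is sqrt(0.60 x 0.40 / 200) = 0.0346, giving a 95% interval of 0.60 ± 1.96 x 0.0346, or 53.2% to 66.8%. This describes a V4 state and contains no change.

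**3. What pooling does to that rate.** Let u be the share of the 200 who are controlled and untreated at V1. The documents do not give u. Assume for illustration that all of them remain controlled at V4, so that all 120 ULRS patients are among the treated:

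- u = 0: 120/200 = 60% of treated patients still uncontrolled
- u = 10%: 120/180 = 66.7%
- u = 20%: 120/160 = 75%
- u = 40%: 120/120 = 100%

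Under this assumption the same overall 60% fits anything from 40% of treated patients gaining control to none. If some untreated patients lose control by V4, the treated figure is lower than shown.

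**4. The V1 rules taken together.** LRS more than 2x/week must be confirmed at V1, yet patients now controlled at V1 continue in the study. If controlled means an ACT of 20 or more, such a patient has a controlled score and confirmed frequent symptoms: a discordant patient under the plan's own rules. If controlled means that the symptoms have resolved, the continuation rule conflicts with the V1 confirmation. The two sections need to be reconciled. Either way, the plan does not say how the constructs relate.

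**5. Possible size of label disagreement.** No agreement figure is given. Assume that 0 to 20% of the 120 ACT-ULRS patients no longer have LRS more than 2x/week, and that 0 to 20% of the 80 ACT-CLRS patients still do.

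- Lowest persistent rate: (120 x 0.80 + 80 x 0)/200 = 96/200 = 48%
- Highest: (120 + 80 x 0.20)/200 = 136/200 = 68%
- Patients classed differently: from 0 to 120 x 0.20 + 80 x 0.20 = 24 + 16 = 40 of 200

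**The case against.** The case for leaving the plan alone is substantial. The protocol defines uncontrolled LRS by ACT, requires a low ACT for entry, uses ACT to allocate study drug at V1, bases its planning rate on ACT and classifies by ACT at V4. Selecting on one measure and classifying control on another is a legitimate design choice. ACT, ASUI and MMRC are all available at V1 and V4, so symptom change can be computed. The V1 frequency questionnaire has no chart row of its own, and the respiratory questionnaire row labelled ASUI is marked at both visits, so the frequency items may already be repeated.

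All of this stands against two stronger readings. A reader might infer that Aim 1 cannot identify controlled and uncontrolled patients, or that the ULRS/CLRS label is invalid. The documents do not support either: the label follows the protocol's own definition of control.

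A reader might also infer from the clinic data that the two criteria are far apart: "56% had persistent cough, 32% had wheeze and 50% had any LRS other than cough", whereas "88% of patients who had ever received ICS or ICS/LABA had an ACT score of" 19 or less. Those figures have different denominators: patients returning for monitoring, and patients who had ever received ICS or ICS/LABA. The share ever treated is not given. If it is 0.50/0.88 = 57% or less, the figures are compatible with no patient having a low ACT without frequent symptoms. Nor do they describe trial patients at V4, who were selected on both criteria.

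The objection does not supply an analysis for SA1.a. Having paired instruments is not the same as planning a paired comparison, and the possible overlap with the ASUI row needs to be confirmed.

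**Conclusion.** The point holds in a limited form. SA1.a has no planned analysis that could answer it: the only SA1 result is a V4 rate, without a V1 contrast and with untreated, already-controlled patients in the denominator. Separately, the match between the ACT label and the entry definition of persistent LRS is not checked, because the frequency measure is not named at V4.

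The size cannot be taken from the documents. The ranges of 0 to 40 of 200 patients classed differently, and 60% to 100% of treated patients still uncontrolled, rest on the assumptions stated with each calculation and are illustrations, not estimates. The second part falls away if the sponsor confirms that the ASUI row includes the V1 frequency items. The first part does not depend on that. This is an inexpensive improvement worth making before V4 data are collected.

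**What to change.** 1. For SA1.a, specify a paired V1-V4 analysis in patients given study drug at V1: mean change in ACT with a confidence interval and a named within-patient test, and the change in the share with ACT below 20. That share is 100% at V1 under the allocation rule, so report the V4 share with its interval and let the ACT score carry the test. Because patients are selected on a low score and there is no comparable untreated group, describe the result as change during treatment.
2. Ask the V1 LRS-frequency items again at V4, or state that the ASUI row already includes them. Report the paired change in the share with LRS more than 2x/week, and cross-tabulate V4 frequency with V4 ACT class.
3. State how the V1 confirmation of LRS frequency and the continuation of patients controlled at V1 fit together.
4. Keep the ACT class as primary. Repeating SA2 to SA4 in patients whose ACT class and frequency agree is optional and has less power than the planned 120 and 80.

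The cost is a few questionnaire items at a visit that already includes questionnaires, and one added analysis. Sample size and classification do not change.
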